## **Treatment Group Comparisons**

For each pain intensity (total; moderate or severe), the percentages of subjects with  $\geq 50\%$  reduction in the number of migraine days per month are compared between each zavegepant treatment group and placebo pooled using Mantel-Haenszel risk estimation with stratification by randomization stratum (yes, no). Percentages are calculated against the number of subjects in the migraine analysis set.

The table displays the following statistics at each month of the DBT Phase and overall DBT by pain intensity:

- Response rate (i.e., "n/N" and percentage), ASE, and 97.5% CI for each treatment group and placebo pooled
- Stratified percentage difference between each zavegepant treatment group and placebo pooled (zavegepanti placebo pooled; i = 100 and 200), ASE, and 97.5% CI
- Response rate (i.e., "n/N" and percentage), ASE, and 97.5% CI by randomization stratum for each treatment group and placebo pooled
- Percentage difference between each zavegepant treatment group and placebo pooled (zavegepanti placebo pooled; *i* = 100 and 200), ASE, and 97.5% CI by randomization stratum.

Results for the endpoint of  $\geq$  50% reduction of moderate or severe pain intensity in the overall DBT support secondary objective #1. Results for all other endpoints support exploratory objective #2.

Note that Protocol Versions 1 to 6 specify to compare treatment groups using a stratified Cochran-Mantel-Haenszel test, which would produce a chi-square statistic. However, this SAP specifies Mantel-Haenszel risk estimation, which is more appropriate given the estimand is based on a difference in percentages between groups.

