9.3.1.2 Secondary Efficacy Endpoints

The proportion of subjects with $\geq 50\%$ reduction from the Observation Phase in the number of moderate or severe migraine days per month over the entire DBT Phase (Weeks 1 to 12) will be analyzed using a Cochran-Mantel-Haenszel test stratified by randomization stratum for the migraine analysis set. Missing data are imputed as non-response (i.e., failure). The difference estimate (zavegepant – placebo), SE, 97.5% CI, and p-value will be reported for each dose of zavegepant versus placebo pooled.

The mean change from the Observation Phase in the number of migraine days per month in the last 4 weeks (Weeks 9 to 12) of the DBT Phase will be assessed for the migraine analysis set from the same GLMEM used for the primary efficacy endpoint.

The mean change from the Observation Phase in the number of migraine days per month in the first 4 weeks (Weeks 1 to 4) of the DBT Phase will be assessed for the migraine analysis set from the same GLMEM used for the primary efficacy endpoint.

The mean number of acute migraine-specific medication days per month over the entire DBT Phase (Weeks 1 to 12) will be assessed for the migraine analysis set using a GLMEM that is

similar in structure to that used for the primary efficacy endpoint, except that the number of acute migraine-specific medication days per month is the dependent variable and there is no covariate. Acute migraine-specific medications are triptans and ergotamine.

The mean changes from baseline in MSQ restrictive role function domain score and MIDAS total score at Week 12 will be analyzed for the DBT efficacy analysis set using GLMEMs that will use the identity link function and include the following variables: Week 12 change from baseline in the score as the dependent variable; baseline score as a covariate; and fixed effects for treatment group and randomization stratum. The Week 12 difference estimate (zavegepant – placebo), SE, 97.5% CI, and p-value will be reported for each endpoint and each dose of zavegepant versus placebo pooled.

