#### **Intercurrent Events**

Intercurrent events are those that occur after treatment initiation and either preclude observation of the endpoint or affect its interpretation.

Study drug discontinuation before the time point of interest defining the endpoint is considered an intercurrent event.

• For efficacy objectives assessed with a continuous endpoint during the DBT Phase, study drug discontinuation is handled with a "hypothetical strategy," i.e., the hypothetical scenario is that had subjects not discontinued DB study drug, their efficacy would have been similar to the efficacy of subjects from the same treatment group and randomization stratum who did not discontinue DB study drug. All observed values of the endpoint of interest are excluded after DB study drug discontinuation (see Section 7.2), and statistical methods are used to estimate the treatment effect that would have been seen had the intercurrent event not occurred.

- For efficacy objectives assessed with a binary endpoint during the DBT Phase, DB study drug discontinuation is handled with a "composite strategy," i.e., the occurrence of the intercurrent event is integrated as a component of the endpoint. All observed values of the endpoint of interest are excluded after DB study drug discontinuation (see Section 7.2), and subjects with missing data are considered failures.
- For safety objectives, study drug discontinuation is handled with a "while-on-treatment strategy". All observed values of the endpoint of interest are used on or before study drug discontinuation + 7 days (see Section 7.2 and the Core SAP).
- For outcomes research and other objectives, study drug discontinuation is handled with a "treatment policy strategy", i.e., the occurrence of the intercurrent event is considered irrelevant, such that all observed values of the endpoint of interest are used regardless of study drug discontinuation.

Non-study prophylactic migraine medication use before the time point of interest defining the endpoint is also considered an intercurrent event. For all objectives, this intercurrent event is handled with a treatment policy strategy, such that all observed values of the endpoint of interest are used.

Nonstudy acute migraine-specific medication use before the time point of interest defining the endpoint is also considered an intercurrent event, except for efficacy objectives based on acute migraine-specific medication days or acute migraine medication days.

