# 3.2.2 Secondary Objective Estimands

The estimands corresponding to the secondary objectives are shown in Table 2.

Table 2 Secondary Objective Estimands

Objective 1	Proportion of subjects with ≥ 50% reduction from the OP in the number of moderate or severe migraine days per month over the entire DBT Phase
Efficacy Endpoint	Proportion of subjects with $\geq 50\%$ reduction from OP in number of moderate or severe migraine days per month over the entire DBT Phase (Weeks 1 to 12)
Summary	Percentages by treatment group, and difference in percentages between treatment groups using Mantel-Haenszel risk estimation with stratification by randomization stratum for the migraine analysis set
Intercurrent Events	Study drug discontinuation: composite strategy
	Non-study prophylactic migraine medication use: treatment policy strategy
	Nonstudy acute migraine-specific medication use: composite strategy
	Use of nonstudy other medication to treat headache (migraine or nonmigraine) or aura: treatment policy strategy
Objective 2	Mean reduction from the OP in the number of migraine days per month in the last 4 weeks of the DBT Phase

Efficacy Endpoint	Mean change from OP in the mean number of migraine days per month in the last 4 weeks (Weeks 9 to 12) of the DBT Phase
Summary	Mean change from OP by treatment group using descriptive statistics and linear mixed effects model with repeated measures, and difference between treatment groups from model for the migraine analysis set
Intercurrent Events	Study drug discontinuation: hypothetical strategy
	Non-study prophylactic migraine medication use: treatment policy strategy
	Nonstudy acute migraine-specific medication use: composite strategy
	Use of nonstudy other medication to treat headache (migraine or nonmigraine) or aura: treatment policy strategy
Objective 3	Mean reduction from the OP in the number of migraine days per month in the first 4 weeks of the DBT Phase
Efficacy Endpoint	Mean change from OP in the number of migraine days per month in the first 4 weeks (Weeks 1 to 4) of the DBT Phase
Summary	Mean change from OP by treatment group using descriptive statistics and linear mixed effects model with repeated measures, and difference between treatment groups from model for the migraine analysis set
Intercurrent Events	Study drug discontinuation: hypothetical strategy
	Non-study prophylactic migraine medication use: treatment policy strategy

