Migraine: Subjects in the DBT efficacy analysis set with  $\geq 14$  days of eDiary efficacy data (not necessarily consecutive) in both the OP and  $\geq 1$  month (4-week interval) in the DBT Phase (see Section 6.3.1). This analysis set is used to assess migraine days, acute migraine-specific medication days, and acute migraine medication days

See Section 7.1 for derived dates and Section 7.2 for analysis periods.

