## 5 SAMPLE SIZE, POWER, AND TYPE 1 ERROR

With a sample size of approximately 480 randomized subjects per zavegepant treatment group and 240 randomized subjects per placebo treatment group, we expect approximately 440 subjects per zavegepant treatment group and 220 subjects per placebo treatment group in the migraine analysis set. Assuming zavegepant provides a 1-day advantage over placebo pooled on the mean change in migraine days per month over the entire DBT Phase (Weeks 1 to 12), common standard deviation of 4.2 days, and a 2-sided  $\alpha = 0.025$  level, then the study has  $\geq 90\%$  power for the primary endpoint. The estimates for the migraine analysis set sample size, mean change in migraine days per month, and standard deviation (SD) are based on observed pooled data from rimegepant study BHV3000-305.

Type 1 error is not applicable. The significance of the primary and secondary endpoints will not be evaluated.

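### Responder endpoints count drug discontinuation and missing data as failure, but their denominator leaves out treated subjects with under 14 on-drug diary days in every double-blind month

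*SAP*

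**What the plan says.** SAP section 3.2 (Intercurrent Events) assigns binary efficacy endpoints a composite strategy for stopping double-blind drug: "the occurrence of the intercurrent event is integrated as a component of the endpoint". Values after discontinuation are dropped, "and subjects with missing data are considered failures". Table 2 repeats this for secondary objective 1 ("Study drug discontinuation: composite strategy"), and Table 3 does so for exploratory objective 2. Protocol section 9.3.1.2 likewise imputes missing responder data as non-response.

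The denominator is set in SAP section 6.3.2.1: "Percentages are calculated against the number of subjects in the migraine analysis set". SAP section 4.1 limits that set to subjects with at least 14 "days of eDiary efficacy data (not necessarily consecutive) in both the OP" and at least one 4-week month of the DBT Phase. Under SAP section 7.2, on-DBT diary data end at the last double-blind dose, or on the day before open-label zavegepant starts if that is earlier.

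SAP section 6.3 lists, among the reasons for exclusion, being treated but having under 14 diary days in all three months. No responder analysis on a wider set is planned. The DBT efficacy analysis set (randomized once, at least one double-blind dose) is already defined, and is used mainly for the outcomes research endpoints.

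**The concern.** A composite strategy with missing counted as failure needs no post-baseline diary data: a subject who stops drug in the first two weeks has a defined outcome, failure. The denominator removes exactly those subjects, and it does so on the basis of what happened after randomization. The primary repeated-measures model is different, because its strategy is hypothetical and a subject with no evaluable month has no outcome to contribute.

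The handling is also uneven within section 6.3.2.1. In the monthly analyses, a subject with under 14 diary days in one or two months is a failure for those months. A subject with under 14 in all three months drops out of the analysis.

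What is at stake is the reported result for secondary objective 1 and its exploratory companions. Leaving failures out of the denominator raises the response rate of any arm that has them, and it raises it more in the arm that loses more subjects early.

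**Working it through.** **Who is excluded.** Count the first double-blind dose as study day 1 (the SAP refers to the Core SAP for the definition of study day). Month 1 is study days 1 to 28. If the last double-blind dose is on day 13, qualifying diary days run from day 1 to day 13: at most 13 in Month 1 and none in Months 2 and 3. The 14-day condition cannot be met. Subjects who stay on drug longer but never reach 14 diary days in a month are excluded in the same way.

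**How many.** SAP section 5 gives 480 randomized per zavegepant group and 240 per placebo group (480 pooled). Of these, "we expect approximately 440 subjects per zavegepant treatment group" and 220 per placebo group (440 pooled) in the migraine analysis set. The plan's power figure reproduces on those numbers:

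- SE = 4.2 × √(2/440) = 0.283
- 1/0.283 = 3.53, and 3.53 − 2.24 (the critical value for two-sided 0.025) = 1.29
- power = 0.901, against the stated 90% or more.

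The expected loss is 40/480 = 8.3% per comparison group. This is an upper bound on the subjects at issue. It also covers subjects never treated, subjects randomized more than once, and subjects with under 14 Observation Phase diary days. The last group should be small, because protocol section 5.3 requires 24 of 28 reports for entry.

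**Effect on the difference.** The documents give neither response rates nor loss by arm, so both are assumed here. Let p1 and p0 be the response rates in the migraine set, and e1 and e0 the fractions added back as failures. The difference becomes p1(1 − e1) − p0(1 − e0). With p1 = 40% and p0 = 30%:

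| Added back as failures (zavegepant / placebo) | Rates | Difference (points) |
|---|---|---|
| none | 40.0% / 30.0% | 10.0 |
| 20 of 460 / 20 of 460 | 38.3% / 28.7% | 9.6 |
| 8.3% / 8.3% | 36.7% / 27.5% | 9.2 |
| 12% / 4.7% | 35.2% / 28.6% | 6.6 |
| 4.7% / 12% | 38.1% / 26.4% | 11.7 |

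With equal loss, the shrinkage is the same proportion at any rates: 10.0 × 440/480 = 9.2 for 30% versus 20% or 50% versus 40% as well. The two unequal rows use about the same total of 80 subjects (0.12 × 480 + 0.047 × 480 ≈ 80).

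To show the range over response rates, suppose the two groups respond equally within the migraine set at rate r, with 60 excluded on zavegepant and 20 on placebo. The wider set then gives r × (420 − 460)/480 = −r/12, which is −1.7 points at r = 20% and −4.2 points at r = 50%.

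**The case against.** The strongest reply is that the migraine set is a deliberate choice. Protocol section 9.3.1.2 names it for this endpoint in the sentence before the missing-as-failure rule, and Table 2 places it beside the composite strategy, so the failure rule can be read as operating inside that set. It follows that the SAP does not depart from the protocol here. The conflict with the composite strategy remains: on that reading, discontinuation counts as failure only for those who first supplied 14 diary days. Both documents share the inconsistency.

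Several stronger inferences are tempting, and the documents do not support them:

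- **That a formal test is compromised.** The endpoint is first among the secondaries in the testing order of protocol section 9.3.1.3, but SAP section 5 (version 9) says significance will not be evaluated.
- **That these subjects go unreported.** SAP section 6.3.1.1 tabulates them for the full analysis set, the section 6.3 listing gives each exclusion reason, and section 6.2.3.3 gives reasons for not completing the phase. A reader could approximate an unstratified failure-imputed rate. It would be rough, because the missing-data table does not separate never-treated subjects, and the stratified difference and its CI could not be rebuilt from the tables.
- **That 8.3% of subjects are early discontinuers, or that the exclusion favours zavegepant.** The first figure is a ceiling, and nothing in the documents gives early loss by arm.

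It is also fair to object that changing the denominator alone would not be enough. The overall-DBT rule in section 6.3.2.1 has no minimum-data condition, so in a wider set a few good prorated diary days could make a responder. The fix has to close that.

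**Conclusion.** The point holds on the text, without any assumed rate: the estimand counts discontinuation and missing data as failure, and the denominator removes the treated subjects with the least data, including everyone whose last double-blind dose is on or before study day 13.

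The size is modest if loss is equal. At assumed rates of 40% versus 30%, the difference moves by at most 0.8 points (10.0 to 9.2), and by less to the extent that the 40 of 480 includes subjects of other kinds. Unequal loss matters more: 6.6 points under an assumed 12% versus 4.7%, or 11.7 with those fractions reversed. Because the rates and the split are assumptions, the actual direction and size are unknown. The change is worth making because it is cheap, it removes a selection on post-randomization behaviour, and no planned output shows the endpoint without that selection.

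**What to change.** In SAP section 6.3.2.1, and in the rows for secondary objective 1 (Table 2) and exploratory objective 2 (Table 3):

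1. Use the DBT efficacy analysis set as the denominator for all responder endpoints.
2. Classify as a failure any subject with under 14 eDiary efficacy data days in the Observation Phase, or under 14 in every DBT month. Apply this to the overall-DBT endpoint as well as the monthly ones.
3. Keep the migraine-set result as a supplementary table, and keep the migraine set for the continuous endpoints.
4. Note the departure from protocol section 9.3.1.2, in the way section 6.3.2.1 already notes its change from the Cochran-Mantel-Haenszel test. Align the set named in sections 4.1, 4.3 and 6.3.2.3.

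The cost is a few sentences, a changed denominator and failure flag in the program, and one added table. Reported response rates will be slightly lower.

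This does not settle one related matter. A subject who stops drug later, say on day 20 with 14 or more diary days, can still be an overall-DBT responder on prorated data. The SAP should say whether that is intended under the composite strategy.

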## 6.3.2.2 Acute Migraine-specific Medication Days per Month in the DBT Phase

During the DBT Phase, subjects may record taking triptan, ergotamine, and other medications to treat headache or aura yesterday in the eDiary headache report.

Acute migraine-specific medication days per month are assessed as "acute migraine-specific medication days per 4 weeks" to correspond with the 4-week visit schedule. Acute migraine-specific medication days per month are based on 4-week intervals, and are prorated to account for missing migraine reports. See Section 9.2.4 for the definition of acute migraine-specific medication days.

Analyses are based on the migraine analysis set using eDiary efficacy data dates in the on-DBT efficacy analysis period.

The number of acute migraine-specific medication days per month in the DBT Phase are prorated to 28 days and derived as follows:

- Month (i.e., 4-week interval) in the on-DBT efficacy analysis period: 28 × (total number of acute migraine-specific medication days in the month)/(total number of eDiary efficacy data days in the month). Subjects must have ≥ 14 days of eDiary efficacy data (not necessarily consecutive) in the specified month to be evaluable.
- Overall DBT: 28 × (total number of acute migraine-specific medication days through Month 3 in the on-DBT efficacy analysis period)/(total number of eDiary efficacy data days through Month 3 in the on-DBT efficacy analysis period).

#### **Descriptive Analyses**

The table of the number of acute migraine-specific medication days per month in the DBT analysis period is provided, and summarizes the parameter descriptively as a continuous variable (including 2-sided normal 97.5% CIs for mean) by treatment group and placebo pooled in each month of the DBT Phase and overall DBT.

#### **Treatment Group Comparisons**

Treatment groups are compared using a linear mixed effects modelwith repeated measures and the following attributes:

- Variables: number of acute migraine-specific medication days per month as the dependent variable; treatment group, randomization stratum, month (i.e., Months 1 to 3 of the DBT Phase), and the month-by-treatment group interaction as fixed effects
- Repeated measures error structure: See Section 6.3.1.3
- SE estimation method: See Section 6.3.1.3.

The table displays the following model estimates:

• LSM, SE, and 97.5% CI by month and overall DBT for each treatment group and placebo pooled

 Difference in LSMs between each zavegepant treatment group and placebo pooled (zavegepanti – placebo pooled; i = 100 and 200), SE, and 97.5% CI at each month and overall DBT. Results in the overall DBT support secondary objective #4, whereas results at other time points support exploratory objective #6.

See Section 9.3.1 for example SAS code. Model estimates by randomization stratum (yes, no) are presented in the same table, using additional models that exclude randomization stratum as a fixed effect.

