## Migraine-related Event Days during the OP

The table of migraine-related event days per month during the OP is provided only for the migraine analysis set, and summarizes the following parameters descriptively as continuous or categorical variables during the OP analysis period:

- Migraine days per month by pain intensity (total; moderate or severe). Categories are < 6,  $\geq 6$ , < 8,  $\geq 8$ , < 12,  $\geq 12$ , < 15,  $\geq 15$ .
- Acute migraine-specific medication days per month. Categories are same as for migraine days per month above.
- Acute migraine medication days per month. Categories are same as for migraine days per month above.

See Sections 6.3.1 for migraine days per month, Section 6.3.2.2 for acute migraine-specific medication days per month, Section 6.3.3.6 for acute migraine medication days per month, and Section 7.2 for the OP analysis period.

Categories may be redefined or combined based on the availability of the data.

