## 6.3.1 Primary Efficacy Endpoint

Subjects are instructed to report headache occurrence, headache pain features and associated symptoms, aura occurrence, and medication used to treat headache or aura in the eDiary headache report every day in the OP and DBT Phase.

Migraine days per month are assessed as "migraine days per 4 weeks" to correspond with the 4-week visit schedule. Migraine days per month are based on 4-week intervals, and are prorated to account for missing migraine reports.

See Section 9.2.2 for the definition of eDiary efficacy data days, and Section 9.2.5 for the definition of migraine days.

The number of migraine days per month in the DBT Phase is examined relative to the number of migraine days per month in the OP for the migraine analysis set, i.e., subjects with  $\geq 14$  days of eDiary efficacy data (not necessarily consecutive) in both the OP analysis period and  $\geq 1$  month (i.e., 4-week interval) in the on-DBT efficacy analysis period.

Months in the DBT Phase are defined as follows:

- Month 1:  $\leq$  4 weeks; study days 1 to 28
- Month 2: > 4 to  $\le 8$  weeks; study days 29 to 56
- Month 3: > 8 to  $\le 12$  weeks; study days 57 to 84.

Analyses are based on eDiary efficacy data dates in the OP and on-DBT efficacy analysis periods.

The number of migraine days per month is prorated to 28 days and derived as follows:

• OP: 28 × (total number of migraine days in the OP analysis period)/(total number of eDiary efficacy data days in the OP analysis period). Subjects must have ≥ 14 days of eDiary efficacy data (not necessarily consecutive) in the OP to be evaluable.

- Month (i.e., 4-week interval) in the on-DBT efficacy analysis period: 28 × (total number of migraine days in the month)/(total number of eDiary efficacy data days in the month).
   Subjects must have ≥ 14 days of eDiary efficacy data (not necessarily consecutive) in the specified month to be evaluable.
- Overall DBT: 28 × (total number of migraine days through Month 3 in the on-DBT efficacy analysis period)/(total number of eDiary efficacy data days through Month 3 in the on-DBT efficacy analysis period).

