#### 6.3.1.3 Treatment Group Comparisons

Analyses are based on the migraine analysis set and total pain intensity, unless specified otherwise.

Main Analysis: Migraine Analysis Set

The main analysis of the primary endpoint uses a linear mixed effects model with repeated measures and the following attributes:

- Variables: change from the OP in number of total migraine days per month as the dependent variable; number of total migraine days per month in the OP as a covariate; treatment group, randomization stratum, month (i.e., Months 1 to 3 of the DBT Phase), and the month-bytreatment group interaction as fixed effects.
- Covariance structure for repeated measures accounting for within-subject correlated errors:
   assumed to be homogeneous across treatment groups, and initially specified as unstructured.
   If the model fails to converge or cannot be fit with an unstructured covariance structure, then
   other covariance structures are specified in the following hierarchical order: Toeplitz (which
   has heterogeneous variances and heterogeneous correlations between elements); first-order
   autoregressive with heterogeneous variances; and first-order autoregressive with
   homogeneous variances.
- SE estimation method: Huber-White "sandwich" (refer to the Core SAP).

Note that Protocol Versions 1 to 6 erroneously specify to include subject as a random effect in the model.

The table displays the following model estimates:

- Least-squares mean (LSM) change from OP, SE, and 97.5% CI by month and overall DBT for each treatment group and placebo pooled
- Difference in LSM changes from OP between each zavegepant treatment group and placebo pooled (zavegepanti placebo pooled; *i* = 100 and 200), SE, and 97.5% CI at each month and overall DBT. Results in the overall DBT support the primary objective, results in the last month support secondary objective #2, results in the first month support secondary objective #3, and results in the second month support exploratory objective #1.

See Section 9.3.1 for example SAS code. Model estimates by randomization stratum (yes, no) are presented in the same table, using additional models that exclude randomization stratum as a fixed effect.

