#### **Treatment Group Comparisons**

Analysis of the restrictive role function domain is based on the DBT efficacy analysis set with paired data, i.e., restrictive role function domain scores at both baseline and Week 12 of the DBT outcomes research analysis period.

Treatment groups are compared using a linear regression model with the following attributes:

- Variables: Week 12 change from baseline in the score as the dependent variable; baseline score as a covariate; treatment group and randomization stratum as fixed effects.
- SE estimation method: See Section 6.3.1.3.

The table provides n (i.e., number of subjects with paired data) and the following model estimates:

- LSM change from baseline at Week 12, SE, and 97.5% CI for each treatment group and placebo pooled
- Difference in LSM changes from baseline at Week 12 between each zavegepant treatment group and placebo pooled (zavegepanti – placebo pooled; i = 100 and 200), SE, and 97.5% CI.

Results support secondary objective #5.

See Section 9.3.2 for example SAS code. Model estimates by randomization stratum (yes, no) are presented in the same table, using additional models that exclude randomization stratum as a fixed effect.

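### Acute migraine-specific medication days are compared without each subject's own Observation Phase value, which the trial already collects, so the 97.5% CIs are probably wider than they need to be

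*SAP*

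**What the plan says.** The endpoint is the mean number of acute migraine-specific medication days (triptan or ergotamine days) per 28-day month over the Double-blind Treatment (DBT) Phase. SAP 6.3.2.2 fits a repeated-measures linear model with "number of acute migraine-specific medication days per month as the dependent variable; treatment group, randomization stratum, month" and the month-by-treatment interaction as fixed effects. Protocol 9.3.1.2 is explicit: the number of such days "is the dependent variable and there is no covariate". Neither document gives a reason.

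The other continuous primary and secondary endpoints are adjusted. The primary model in SAP 6.3.1.3, which also supplies secondary endpoints 2 and 3, has the "number of total migraine days per month in the OP as a covariate". The MSQ model in SAP 6.5.1, reused for MIDAS in 6.5.2, has the "baseline score as a covariate; treatment group and randomization stratum as fixed effects".

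The missing covariate is already collected. SAP 6.3.1 has subjects report "medication used to treat headache or aura in the eDiary headache report every day in the OP and DBT Phase", and SAP 9.2.1 shows separate triptan and ergotamine questions. Membership of the migraine analysis set (SAP 4.1) requires at least 14 "days of eDiary efficacy data (not necessarily consecutive) in both the OP and" at least one month of the DBT Phase. SAP 6.2.5.2 tabulates the OP value for this same set and directs the reader to "Section 6.3.2.2 for acute migraine-specific medication days per month". That section supplies formulas for treatment only: "The number of acute migraine-specific medication days per month in the DBT Phase are prorated to 28 days and derived as follows".

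**The concern.** Subjects differ widely and persistently in how often they take acute medication. With no OP term, that between-subject spread stays in the residual variance and widens the interval for each zavegepant minus pooled placebo difference. Randomization is stratified only on stable prophylactic use (SAP 2.2), so the model also leaves any chance imbalance in OP acute medication use uncorrected.

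What is at stake is precision, not validity. SAP 5 says significance will not be evaluated, so no test is lost. But the estimate and its 97.5% CI are then the whole inferential result for secondary objective 4 (overall DBT) and for the by-month results under exploratory objective 6. The by-stratum models in the same table have the same omission.

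**Working it through.** **Inputs**

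- Planned migraine analysis set: 440 per zavegepant group and 2 x 220 = 440 pooled placebo (Protocol 9.1, SAP 5).
- Two-sided 97.5% CI (SAP 6.3, 6.3.2.2), so z = 2.2414.
- The documents give neither an SD for this endpoint nor an OP-to-DBT correlation. Half-widths are therefore in SD units, and rho is an assumption shown over a range.

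**The plan's own figure.** The only stated precision figure is at least 90% power for the primary endpoint (1-day difference, SD 4.2, two-sided 0.025).

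- SE = 4.2 x sqrt(2/440) = 0.2832.
- 1/0.2832 - 2.2414 = 1.290, which gives power 0.9015.

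The figure reproduces, which confirms that 440 versus 440 with z = 2.2414 is the basis to use. It says nothing about medication days.

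**Effect of the covariate.** Let rho be the correlation, within treatment group and stratum, between the OP value and the DBT value being estimated. With complete data, adjustment multiplies the SE of the difference by sqrt(1 - rho^2); with missing months this is approximate. The unadjusted half-width is 2.2414 x sqrt(2/440) = 0.151 SD. The last column is 440/(1 - rho^2), the unadjusted group size that would give the same width.

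| Assumed rho | Width ratio | CI narrower by | Half-width (SD) | Equivalent n per group |
|---|---|---|---|---|
| 0 | 1.000 | 0% | 0.151 | 440 |
| 0.3 | 0.954 | 4.6% | 0.144 | 484 |
| 0.5 | 0.866 | 13.4% | 0.131 | 587 |
| 0.6 | 0.800 | 20.0% | 0.121 | 688 |
| 0.7 | 0.714 | 28.6% | 0.108 | 863 |
| 0.8 | 0.600 | 40.0% | 0.091 | 1222 |

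For scale only, borrowing the primary endpoint's SD of 4.2 days: the half-width is 0.635 days unadjusted, 0.550 at rho 0.5 and 0.453 at rho 0.7.

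**Overall DBT.** The 12-week mean is less noisy than one month, so its correlation with the OP value is higher than a single month's. If all pairs of 4-week periods share one correlation r (a further assumption), the variance of the three-month mean is (1 + 2r)/3 and rho = r/sqrt((1 + 2r)/3).

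- r = 0.3: rho = 0.41, CI 8.8% narrower.
- r = 0.5: rho = 0.61, CI 20.9% narrower.
- r = 0.7: rho = 0.78, CI 37.8% narrower.

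**Do skewed counts break the formula?** A simulation used zero-inflated day counts, three groups of 440, linear regression on the 12-week mean and sandwich SEs. Observed correlations of 0.41, 0.65 and 0.81 gave SE ratios of 0.913, 0.758 and 0.590, which match sqrt(1 - rho^2). With a true difference of zero, the mean estimates stayed near zero with and without the covariate.

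**Is the value available for everyone analysed?** Yes. The endpoint is analysed in the migraine analysis set, and nobody enters that set without at least 14 OP diary days.

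**The case against.** The strongest reply is that the choice is deliberate and harmless. Protocol and SAP agree, and the protocol states it outright. SAP 6.3.2.3 places this endpoint alone among those not involving change from OP or baseline, and the revision history shows the section was revisited in Version 7. The study ended early for business reasons, no significance is evaluated, and no decision rests on this interval. The size of the gain depends on an undocumented correlation. A further SAP version and another departure from the protocol are not quite free.

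Most of that is right about consequence: this is not an error, a bias or a lost test, and the gain cannot be fixed at one number. It does not answer the point.

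- Analysing a value instead of a change does not prevent adjustment for the OP value. In a linear model the mean difference being estimated stays the same.
- A correlation near zero is unlikely. The same diary questions are asked in both periods, and subjects continue their usual acute medication. Because Protocol 5.4 prohibits ergotamine from Screening, the endpoint is largely triptan days. Protocol 5.2 admits subjects with triptan contraindications, who would be expected to score near zero in both periods.
- The percentage gains do not depend on the final sample size.

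One possible argument carries no weight. The example code in SAP 9.3.1 lists an OP covariate, but its variables are those of the primary endpoint, so it shows nothing about the model intended here.

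**Conclusion.** The point holds as a recommended improvement in precision. The model omits an OP value that exists for every analysed subject, and including it narrows the 97.5% CI whenever that value correlates with the DBT value. The saving is modest at rho 0.3 and large at 0.7 or above. It rests on the assumed rho and, for the overall-DBT figures, on a common correlation between periods. The absolute half-widths use the planned 440 versus 440; the documents give no final number. That the covariate is missing from the model and available in the data is certain; the practical size of the gain is not. The existing unadjusted analysis remains valid.

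**What to change.** In SAP 6.3.2.2:

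1. Add the number of acute migraine-specific medication days per month in the OP as a covariate, in both the overall and the by-stratum models, and state it explicitly for this endpoint.
2. Add the OP derivation that SAP 6.2.5.2 looks for there: 28 x (acute migraine-specific medication days in the OP analysis period)/(eDiary efficacy data days in the OP analysis period), with at least 14 days required. This parallels the migraine-day formula in SAP 6.3.1, and the baseline table needs it whatever is decided about the model.
3. Note the departure from Protocol 9.3.1.2, as the SAP already does for the random effect (6.3.1.3) and the Cochran-Mantel-Haenszel test (6.3.2.1).

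The change must be fixed before unblinding at the LSLV database lock (SAP 2.3). If that has passed, keep the unadjusted analysis as planned and label the adjusted one supplementary.

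The cost is a short SAP amendment and one degree of freedom. No new data are needed and no analysed subject is lost. The endpoint stays a value, so the estimand and the summary table layout in SAP 6.3.2.3 are unchanged.
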